We expect that exciting the matrix cell-rich areas of the thalamus, such as the ventral anterior section, will lead to a decrease in criterion (c), indicating a shift of the decision criterion towards a more liberal response bias. Conversely, exciting the core cell-rich areas of the thalamus, like the dorsal posterior section, will increase sensitivity (d'), resulting in improved differentiation ability in stimulus perception. Conversely, we also anticipate that inhibiting the ventral anterior thalamus will have the opposite effect on criterion (c), leading to a more conservative decision bias. Inhibiting the dorsal posterior thalamus will reduce sensitivity (d'), resulting in a decreased ability to differentiate between stimuli. By observing these effects, we aim to unravel the distinct causal roles of the anterior and posterior thalamus in conscious perception. This disentanglement will provide valuable insights into the mechanisms of specific thalamic regions in shaping perceptual processes.

Number of Subjects, Recruitment and Informed Consent

Our study will involve the enrollment of 60 participants, who will be randomly assigned to two groups, with each group consisting of 30 participants. The participants will be divided based on the type of transcranial LIFUP they will receive, either excitation or inhibition, targeting four specific thalamic areas. See experimental design details below. Healthy participants will be recruited by listing on UMClinicalStudies.org and by postings at area colleges and community groups in Ann Arbor. Interested volunteers will call the phone number of a designated recruiter for an initial phone screening. The initial phone screening will consist of questionnaires related to medical history, demographic information, handedness, inclusion and exclusion criteria. If interested, the participant will

complete the questionnaires, which will be reviewed by the study team. Once eligibility is confirmed by the study team, the one-time research study session will be scheduled. Participants may be screened for COVID-19 prior to entry into the hospital per hospital guidelines.

[figure not shown]

Figure 3. Randomized study group assignment. A total of 60 participants will be enrolled in the study and randomly assigned to two groups, each comprising 30 participants. The group assignment will be based on the type of transcranial LIFUP they will receive, either in the form of excitation or inhibition.

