All participants will give written informed consent according to institutional guidelines prior to any testing. The Principal Investigators or their designee will obtain consent using a written consent form approved by the Institutional Review Boards of the University of Michigan Medical School (IRBMED). It will contain detailed information regarding the purpose, risks and benefits of participating. Copies of the signed consent form will be given to the subjects; the original consent will remain with the study team.

Compensation

Participants will be compensated \$100 for completing the one-time visit. Participants who have shaved or no hair, or those willing to shave the right side of their temple will be compensated an additional \$75. Participants who are willing to shave an area around their right side of their temple should do this prior to arriving to their scheduled study visit.

Inclusion and Exclusion Criteria

Volunteers are screened using a medical history and demographics questionnaire.

Inclusion Criteria:

- Healthy adults ages 18 – 40.
- Must be right-handed.
- Must have normal or corrected-to-normal vision (while wearing contact lenses).
- Must not be on any medications for any neurological, psychological, or psychiatric conditions.
- Must be English speaking.
- Must be capable of giving written informed consent.

Exclusion Criteria:

- Vision that is not 20/20, or vision that is not corrected to 20/20 while wearing contact lenses.
- History of significant head injury with loss of consciousness.
- Learning disability or other developmental disorder.
- Any impairment (sensory or motor loss), activity, or situation that in the judgment of the study coordinator or Principal Investigators would prevent satisfactory completion of the study protocol.

Methods and Procedures

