Our participant recruitment will be inclusive, encompassing individuals of all sexes and diverse ethnic/racial backgrounds, with the goal of achieving equal representation and promoting diversity. However, to minimize age-dependent variation in LIFUP effects, the age range of participants will be restricted to 18-40 years. This limitation will help ensure a more homogeneous sample for our study, enabling us to focus to reliably determine specific effects of LIFUP on conscious perception within the limitation of sample size.

Human Studies and Safety Profile related to LIFUP

LIFUP has been shown to be a safe and effective method to modulate human brain activity, when the stimulation parameters and protocol follow the available guidelines ^{24,43,44}. The majority of studies with ultrasound have reported no adverse events or evidence of anatomical damage ^{35,45-50}. Mild and moderate symptoms have been occasionally reported, such as neck pain, sleepiness, muscle twitches, itchiness, and headaches ⁵¹. However, a comprehensive safety survey focusing on ultrasound for human neuromodulation found no evidence of serious adverse effects in a large cohort

of participants⁵². Out of 120 participants, 64 responded to a follow-up questionnaire, and none experienced serious adverse effects. Only 7 out of the 64 participants reported mild to moderate symptoms (e.g., neck pain, attention problems, muscle twitches, and anxiety) that were perceived as 'possibly' or 'probably' related to their participation in LIFUP experiments. Notably, common unrelated symptoms included sleepiness and neck pain. Initial transient reports of mild neck pain, scalp tingling, and headaches were extinguished upon follow-up, with no new symptoms reported up to one month after the study⁵². Furthermore, studies have not shown any LIFUP-induced tissue damage in the absence of heating, except in cases where contrast agents were used to enhance cavitation effects²⁶. Additionally, LIFUP has been shown to be safe even at intensities several times higher than the FDA limit for diagnostic ultrasound (720 mW/cm^2)⁵³. Overall, the available evidence indicates that LIFUP is a safe and well-tolerated method for human neuromodulation, provided the proper guidelines and parameters are followed.

Justification for the Risks Involved

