The proposed procedure entails minimal risks, while the potential knowledge gains hold significant importance for humanity. As a result, the risk-to-benefit ratio is very low. These experiments offer a unique opportunity to understand the neuromodulation's impact on human conscious perception. The potential insights gained from this study justify the minimal risks involved, making it a valuable and worthwhile endeavor.

Procedures for Minimizing Risks

All research subjects will undergo a thorough screening process to ensure they meet the inclusion and exclusion criteria. Additionally, if any subjects express or exhibit anxiety related to the LIFUP procedure, they will have the opportunity to discuss their feelings or withdraw from the experiment if they wish.

We are committed to strictly adhering to the FDA limit for diagnostic ultrasound intensity (as outlined in the FDA guidance document on diagnostic ultrasound systems and transducers) during the LIFUP procedure to maintain safety and prevent any adverse effects. The FDA previously determined that the use of LIFUP in our studies carries nonsignificant risk (NSR).

Adverse Events

Adverse events will be monitored throughout the procedures and for 24 hours after the procedure via a phone call to the subjects. We will follow their medical record for 30 days following the procedure. Complications or adverse events that are observed by the investigator or reported by the subject will be recorded. For all adverse events and complications, a description of the event, date first observed, any action taken, and ultimate outcome will be recorded.

For all adverse events, sufficient information will be pursued and/or obtained as to permit 1) an adequate determination of the outcome of the event (i.e., whether the event should be classified as a serious adverse event) and; 2) an assessment of the causal relationship between the adverse event and the investigational device, or if applicable, the other study treatments of diagnostic product(s). Adverse events felt to be associated with the investigational device, or if applicable, other study treatment or diagnostic product(s) will be followed until the event (or its sequelae) or the abnormal test finding resolves or

stabilizes at a level acceptable to the sponsor-investigator. Adverse events will be reported to the IRB according to their reporting guidelines.

Serious and Unanticipated Adverse Device Events

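### Between the 24-hour call and day 30, the only planned source of adverse events is a medical record that participants need not have, so late-onset symptoms may be missed.

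*Combined protocol and SAP*

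**What the plan says.** The Adverse Events section of the combined protocol and SAP describes follow-up in two planned steps. First: "Adverse events will be monitored throughout the procedures and for 24 hours after the procedure via a phone call to the subjects". Second: "We will follow their medical record for 30 days following the procedure". It then gives a general rule with no time limit: "Complications or adverse events that are observed by the investigator or reported by the subject will be recorded". Events judged related to the device "will be followed until the event (or its sequelae) or the abnormal test finding resolves or" stabilises.

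On the population, the section on number of subjects and recruitment says: "Healthy participants will be recruited by listing on UMClinicalStudies.org and by postings at area colleges and community groups in Ann Arbor". That section schedules a single study session. The Inclusion and Exclusion Criteria admit healthy adults aged 18 to 40 and state: "Volunteers are screened using a medical history and demographics questionnaire". No listed criterion concerns a record at the institution or access to an outside one.

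The plan does not say which record is meant, how it is opened, or how a participant without one is classified. It specifies no safety analysis and no denominator for adverse events.

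**The concern.** Record follow-up suits patients who receive their care at the study site. These participants are healthy volunteers who come once, and some may have no record that the team can read. For such a person, the 30-day step gives no information if applied as written. With no rule for that case, a blank from a participant who could not be observed looks the same as a blank from one who was observed and well.

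The source also suits the expected symptoms poorly. The section on human studies and the safety profile lists complaints such as headache, neck pain, itchiness, muscle twitches, anxiety and attention problems. It is reasonable to expect that some of these would never be brought to a clinic, although the documents give no figure for this. The safety survey cited in that section used a follow-up questionnaire and reports on symptoms up to one month. The reassurance on which the plan relies was thus obtained by asking people, and the plan does not ask its own participants after 24 hours.

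At stake is the completeness of the safety data after thalamic sonication at four sites in one visit. Following an event to resolution, and the 10-working-day report of serious unanticipated events, both start only once the event is known.

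**Working it through.** The plan gives no adverse-event rate, record coverage or detection probability for its own participants, so there is no stated figure to reproduce. The check sets the passages side by side and then illustrates what incomplete coverage does.

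**Who is asked, and when**

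| Period | Planned source | Prompted? |
|---|---|---|
| Study session | Monitoring during the procedures | Yes |
| To 24 hours | One phone call | Yes |
| 24 hours to day 30 | Medical record | No |
| Any time | Participant's own report or investigator observation | No |

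The period without scheduled contact is 30 − 1 = 29 days. With a single session, there is no later visit at which the investigator could observe an event.

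**Does every participant have a readable record?** The recruitment text and the listed criteria do not ensure it. Medical history at entry comes from a questionnaire, so eligibility does not depend on a record either.

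**Illustration of coverage.** The inputs are 60 participants (2 × 30, from the recruitment section) and an assumed share with a readable record. If no event is seen among n observed participants, the exact one-sided 95% upper bound for the true rate is 1 − 0.05^(1/n).

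| Assumed coverage | n | Upper bound if zero events seen |
|---|---|---|
| 100% | 60 | 4.9% |
| 75% | 45 | 6.4% |
| 50% | 30 | 9.5% |
| 25% | 15 | 18.1% |
| 10% | 6 | 39.3% |

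These bounds assume that every event in a person with a record is entered in it. If only a share s is entered, the bound becomes [1 − 0.05^(1/n)] / s. With s = 0.5 (also assumed), n = 60 gives 0.0487 / 0.5 = 9.7%, and n = 30 gives 0.0950 / 0.5 = 19.0%.

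The documents supply neither the coverage nor s. The tables show how the strength of a zero count depends on them; they do not estimate how many events would be missed.

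**The case against.** The strongest reply has four parts.

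- **The record is not the only route.** Events that a participant reports are recorded whenever the report comes. This stands, and the point is limited accordingly. However, nothing prompts such a report after the call.
- **Known symptoms are not lost.** A reader might infer that persisting symptoms go undetected. The documents do not support that: a symptom identified at the visit or on the call, if felt to be related, is followed until it resolves or stabilises. The gap concerns symptoms that begin after the call or were not mentioned on it.
- **Few late events may occur.** The safety section says of the cited survey: "Only 7 out of the 64 participants reported mild to moderate symptoms". A reader might apply 7/64 to the 60 participants and treat the product as the number missed. That is unsupported. The text does not say when those symptoms began, some would be caught at the visit or the call, and the same section states that no new symptoms were reported up to one month. That last statement does count against a large gap. It comes from a survey with 64 of 120 responding (53%), so it lowers the expectation of late events without replacing ascertainment in this trial.
- **Access may be settled elsewhere.** The consent form is not part of the available text and may contain a record release or instructions on reporting late symptoms. Its absence here is no evidence of a defect. A release would still not create a record for someone who has none, or capture a symptom never brought to care.

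It can also be said that this is a nonsignificant-risk, single-visit study whose outcomes are c and d', so that a further contact is a matter of preference. The low risk limits the weight of the point. It does not make the stated 30-day method workable for every participant.

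**Conclusion.** The point holds as a gap in safety ascertainment. Apart from unprompted reports, the planned information for 29 of the 30 days comes from a source that participants are not required to have. For some of them no entry cannot be told from no event, and symptoms starting after the call, especially mild ones, may be missed.

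Its size cannot be estimated from the documents. A reader might infer that more than half of later events would go unseen. That would require the product of record coverage and the share of events entered in a record to fall below 50%, and neither quantity is given. A reader might also infer that missed events will be reported as none. The plan contains no safety analysis or reporting rule from which to conclude that; the supportable statement is that it has no rule to prevent it.

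The conclusion rests on the recruitment and eligibility text as it stands, and on the expectation that some mild symptoms do not lead to a clinic visit. It concerns safety reporting only.

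**What to change.** Keep the 24-hour call. Add one short contact with every participant at day 30, by phone or e-mailed symptom questionnaire, using the same items as the call. Keep record review as a supplement where a record exists, and state which record is meant. Report 30-day events over the number of participants actually reached, and give the number not reached separately.

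The cost is about 60 brief contacts by existing staff and a minor amendment. Participants carry a slight extra burden, and the reported rate of mild events may rise because people are asked. The d' and c analyses do not change.
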